#### **10.3.10. Other Components of Data Management Plan**

**Randomization and Data Collection:** Each subject is assigned a unique study number by the EDC, which provides a centralized, web-based randomization system. Treatment allocations will be stratified and centralized across all study centers. Daily data collection of ICP management, ICU care, catheter monitoring, and neuroimaging will assess the subject's clinical response to treatment as part of the clinical trial. This data will be used to assess compliance with the study protocol, intervention stopping rules, and care directed at independence. Daily results of routine hematology, chemistry, and coagulation studies also will be collected if reported.

**Protocol Compliance:** Procedures will be implemented to maximize adherence to the protocol (meetings, communications via website and teleconferences, individual and group training, MOP, and SOP documents). Comprehensive training (approximately 20 hours each for both the coordinator and investigator, one to 10 hours each for other site staff) is required before a site is activated. Early review of data is made possible by real-time entry of data into a database with validations and daily monitoring. This is particularly important with respect to the mRS, our primary endpoint, as rapid central review is anticipated to allow for repeat interview of the subject should an incomplete exam be documented. Site investigators are required to report a protocol deviation within 24 hours of occurrence or as soon as it is discovered. If the QA monitor discovers an undocumented major deviation during a monitoring activity, the monitor will notify the CCC immediately. Each site coordinator will report deviations as they are discovered to the local IRB in accordance with local requirements. While there may be rational clinical reasons for an occasional deviation, a site with serious, continual problems is at risk for losing its funding. Routine reporting of protocol deviations will be made to the NINDS, DSMB, and other regulatory agencies as required by GCP.

**FDA Guidance for Electronic Data Entry Compliance:** The design and development of the electronic database system will reflect the FDA Guidance for Industry for Computerized Systems Used in Clinical Trials (April 1999) as well as the Electronic Records/Electronic Signatures rule (21 CFR part 11). The system is currently in use with the CLEAR III trial and the earlier MISTIE II study. A secure, computer generated, time-stamped electronic record will allow reconstruction of the course of events relating to the creation, modification, and deletion of an electronic record. Source documents will be retained to enable a reconstruction and evaluation of the trial. The system will ensure that all applicable regulatory requirements for record keeping and record retention in clinical trials are met with the same degree of confidence as are provided with paper systems. Clinical investigators will retain the original copy of all source documents uploaded onto the eCRF. Query resolution correspondence will be maintained and eCRF edits will be

tracked by the system. Changes to a required record will not obscure the original information. The record will clearly indicate the time a change was made and clearly provide a means to locate and read the prior information through the audit trail. This audit trail will be in compliance with the 21 CFR 11.10(e). The record, along with supporting documentation, will also indicate who made the changes, when changes were made. Security measures will be in place to prevent unauthorized access to the system and data. To ensure that individuals have the authority to proceed with data entry, the system will be designed to verify the electronic signature (user ID and password) at the start of a user session. The data entry system will ensure attributability. Each entry to an electronic record, including any change, will be made under the electronic signature of the individual making that entry. A separate electronic signature will not be required for each entry or change; a single electronic signature will cover multiple entries or changes. Individuals who maintain the electronic record systems as well as the audit trail will carry the responsibilities to protect authenticity, integrity, and confidentiality of electronic records. Audit trails will be available for FDA inspectors at the study site or any other location where associated electronic study records are maintained. The system will be designed to contain the prompts, lookup values, cross-field validations, flags, and on-line help to encourage consistent use of clinical terminology and to alert the user in case that data entered are out of acceptable range. External safeguards will be in place to ensure that access to the computerized system and to the data is restricted to authorized personnel. Servers will be stored in a physically secured, guarded data center.

**Security Measures:** Users at the participating centers will be aware of system security measures and the importance of limiting access to authorized personnel. SOPs will be in place for handling and accessing the system to prevent unauthorized access. Access to the data at a clinical site will be restricted and monitored by the system through required log-on, security verification procedures, and audit trail. The data cannot be altered, browsed, queried, or reported via external software applications without entering through the protective software, although computers at each site may also be used for the purposes other than the clinical study. Because the system will be largely through remote access, all data and applications used for the study will be logically and physically isolated in the servers in order to preclude unintended interaction with non-study use software. These servers will be strictly monitored and maintained by designated administrators at an independent third party (e.g., only Prelude Dynamics, the contracted EDC vendor, has password access to the database and only its contracted commercial data center, On-Ramp Systems both of Austin, Texas, has access to the physical hardware); neither remote sites nor any member of the project team will have the ability to change such logical security of the system. Written procedures describing contingency plans for continuing the study by alternate means in the event of hardware or facilities failures with alternate hardware or at an alternate site will be provided to each site. It should be noted that the data management procedures will reflect the advanced use of computer and software technology; include database technology, and electronic file management principles; and therefore be of the highest possible standards achievable for data security and information integrity. Specifically, the data center is SAS-70 Type II compliant, HIPAA-audited and certified for maintenance of banking, credit card, and PHI).

**Backup Recovery:** Records will be backed up daily to prevent a catastrophic loss compromising the quality and integrity of the data. Data will be backed up onto digital media which will be stored at an offsite location. Backup and recovery logs will be maintained to facilitate an assessment of the nature and scope of data loss in the event of a system failure. Special backup plans for video files at the Glasgow data center will include secure offsite tape backup; no clinical data other than the Rankin video interview and associated tracking (blinded patient number, visit date, investigator's score, site, and interviewer name) is stored on the Glasgow system and the Outcomes Center has no access to the EDC database.

**Limited Access:** Each user will be assigned an individual account with a unique username and password. Any user will be locked out after 10 consecutive attempts, with any unauthorized access attempt recorded in a log file. Users will be required to exit the system upon leaving a workstation. The computer will automatically log off the current session when an idle period reaches 30 minutes. For short periods of inactivity, the automatic screensaver will be password protected to prevent unauthorized access to the system.

**Audit Trails:** All changes made to data in the electronic record are tracked and recorded in the audit trail. This audit trail will capture the date/time, the contents of the changes made, and the login id used to make the change. The audit trails will be created incrementally in chronological order, with prevention of overwrite, as such data overwriting is in violation of §11.10(e). Audit trail information will be reviewed by pre-authorized personnel if the need arises to verify the quality and integrity of the data.

**Date and Time Stamps:** All data will be saved on a central server carrying a time stamp, which will be documented in the audit trail. The EDC software will display the participating site's time zone but record transactions in exact U.S. Central Time as the server is located in that time zone. The date and time on the server will be synchronized to the time provided by the U.S. National Institute of Standards. Individual users will be unable to change the time on the server. Patient procedure times will be collected in local time and recorded in the patient medical record, such as the date/time of a CT scan, lab draw or dose. The site's clocks are not synchronized to any particular standard or even synchronized within the site, but such exactness is immaterial for this study, consistent with the GCP norms for all multicenter clinical trials and otherwise beyond the reasonable control of the CCC.

## 10.4 Adverse Experience Reporting

### 10.4.1. Assessment of Safety

#### Specification of Safety Variables

Safety assessments will consist of monitoring and reporting adverse events (AEs) and serious adverse events (SAEs), all events of death, and any study specific issue of concern.

### **Adverse Events**

**AE definition:** An adverse event is any untoward medical occurrence in a patient entered into the study that does not necessarily have a causal relationship with this treatment. An adverse event can be any unfavorable and unintended sign (including an abnormal lab finding), symptom, or disease temporally associated with the use of the product or treatment, whether or not related to the product or treatment. The investigator must follow adverse events to resolution whenever possible.

AEs include the following:

- AEs not previously observed in the subject that emerge during the protocol-specified AE reporting period, including signs or symptoms associated with intracerebral hemorrhage that were not present prior to the AE reporting period.
- Complications that occur as a result of protocol-mandated interventions (e.g., invasive procedures such as catheter placement). Preexisting medical conditions (other than the condition being studied) judged by the investigator to have worsened in severity or frequency or changed in character during the protocol-specified AE reporting period.

### **Serious Adverse Events**

**SAE definition:** A serious adverse event is an adverse event that results in any of the outcomes listed below. For purposes of this study, Regulatory Agency reporting responsibilities have been designated to the Coordinating Center.

1. Results in death (i.e., the AE actually causes or leads to death). Study Chair agrees to adhere to FDA-defined guidelines and submit an *expedited* report of any death that is *related* (even remotely) to study drug or the MIS procedure and *unexpected* if the death occurs within 30 days from the date of the original ICH event.
2. Life threatening (i.e., the AE, in the view of the investigator, places the subject at immediate risk of death. It does not include an AE that, had it occurred in a more severe form, might have caused death.).
3. Requires inpatient hospitalization or prolongs inpatient hospitalization.
4. Persistent or significant disability or incapacity: a substantial disruption of a person's ability to conduct normal life functions
5. A congenital anomaly or birth defect in a neonate/infant born to a mother exposed to the rt-PA.

6. Considered a significant medical event by the investigator based on medical judgment (e.g., may jeopardize the subject or may require medical/surgical intervention to prevent one of the outcomes listed above).

**Medical events of interest (MEOI) definition:** MEOIs must be reported to the CCC for Medical Monitor and Safety Event Committee review. The AE dictionary, which drives the drop down lists on the AE screen in the EDC system, pre-specifies which events are defined as MEOIs. A MEOI may or may not satisfy the definition of a SAE but will be reported using the same SAE reporting screen in the EDC system and will undergo the same review as a SAE. In summary, the MEOIs for the trial are as follows:

1. Ventriculitis/Cerebritis/Meningitis
2. Cerebral bleeding events (asymptomatic and symptomatic)
3. Any AE or SAE deemed by the site PI or Medical Monitor as possibly, probably, or definitely related to the MIS procedure or rt-PA administration(s)
4. Any AE or SAE requiring discontinuation of dosing or withdrawal from follow-up

**Adverse event intensity grading:** A coding dictionary, based on the CTCAE dictionary, is developed and will be used at the site-level to code in the EDC system adverse events as they occur. The dictionary assigns an intensity code to each event term. The intensity codes are event term-specific and usually range from 1-5, with 1 being mild and 5 being death. Certain AEs in the coding guide are defined as potentially serious SAEs if there is a medically qualifying factor. All AEs coded as a grade 4 or 5 will automatically require SAE reporting. These events will be reviewed by the Medical Monitor and, as needed, the Safety Event Committee.

#### **10.4.2. Assessment of Adverse Events**

All AEs and SAEs whether volunteered by the subject, discovered by study personnel during questioning, or detected through physical examination, laboratory test, or other means will be reported appropriately. Each reported AE or SAE will be described by its duration (i.e., start and end dates), regulatory seriousness criteria if applicable, suspected relationship to the MIS procedure and the rt-PA administration(s) (see following guidance), and actions taken.

**Attributability of AEs to the MIS procedure/rt-PA administrations:** Adverse events occurring more than 7 days after the MIS procedure are not expected to be considered related to the procedure. Also, due to the relatively short half-life of rt-PA, adverse events occurring more than 72 hours after completion of the last rt-PA administration are not expected to be considered related to the rt-PA administration(s). The investigator and/or Medical Monitor will define whether the event is best described as UNRELATED, POSSIBLY related, PROBABLY related, or DEFINITELY related to the MIS procedure

and/or the rt-PA administration(s) according to the following definitions. To ensure consistency of AE and SAE causality assessments, investigators should apply the following general guideline:

**Yes**

There is a plausible temporal relationship between the onset of the AE and the administration of the rt-PA, and the AE cannot be readily explained by the subject's clinical state, intercurrent illness, or concomitant therapies; and/or the AE follows a known pattern of response to the rt-PA; and/or the AE abates or resolves upon discontinuation of the rt-PA.

- **Possibly Related:** The adverse event has a temporal relationship to the MIS procedure or the rt-PA administration(s). However, an alternative etiology may be responsible for the adverse event. Information on drug withdrawal may be lacking or unclear.
- **Probably Related:** The adverse event has a temporal relationship to the MIS procedure or the rt-PA administration(s). The event is unlikely to be related to an alternative etiology. There is a reasonable response on withdrawal (dechallenge). Rechallenge information is not required.
- **Definitely Related:** The adverse event has a temporal relationship to the MIS procedure or rt-PA administration(s) and resolves when rt-PA administration is discontinued. An alternative etiology is not apparent.

**No**

Evidence exists that the AE has an etiology other than the rt-PA (e.g., preexisting medical condition, underlying disease, intercurrent illness, or concomitant medication); and/or the AE has no plausible temporal relationship to rt-PA administration (e.g., cancer diagnosed 2 days after first dose of study drug).

- **Unrelated:** There is evidence that the adverse event definitely has an etiology other than that assigned to either the MIS procedure or rt-PA administration(s).

**Unexpected AE definition:** Unexpected events are any adverse events in which the specificity or severity is not consistent with the natural history of ICH without the test intervention including catheter placement and rt-PA administration. Unexpected will be defined as the specificity or severity of an event that is not consistent with the risk information described in this protocol.

**Expected AE definition.** The Medical Events listed in Appendix 5 are published by the American Stroke Association and the European Stroke Initiative as natural history events of ICH/IVH or are found in the Investigator's Brochure or Alteplase Package Insert or Product Monograph for the use of rt-PA. These medical events are therefore expected in

the disease process or with use of rt-PA. Please enter these expected events on the Adverse Event form if they occur. Reports of these events will be analyzed and submitted as grouped data by the trial's statisticians.

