After placement of the catheter and a CT scan to confirm correct placement, a six-hour post-surgical stabilization period is required prior to first injection of rt-PA. Keep the drainage system to drainage for six hours post catheter placement *prior* to first dose of rt-PA. This time is mandated to reduce the possibility of secondary hemorrhage. If new bleeding or bleeding expansion is seen on the post-op CT scan, wait 12 hours and repeat the CT scan. When the bleeding is stable, dosing can be initiated.

If post-operative clot volume is 10 to 15 mL, rt-PA should not be given. The catheter should remain in place and open to drainage for 24-36 hours prior to removal.

**Catheter adjustment/replacement:** Correct catheter placement will be CT-confirmed locally and post-operative measurements will be repeated centrally by the Surgical Center. Catheter adjustments will be made at this time, if necessary. If the hematoma appears larger or the shape is altered on CT scan after the catheter is placed, the catheter may require repositioning and a post-repositioning CT scan to confirm correct placement within the clot as well as stability of clot size. Repositioning is defined as the partial removal or “pull back” of the non-optimally placed catheter. Replacement is defined as removal of the catheter and replacement with a better targeted catheter using the introducer method described above with either the same or a different trajectory of insertion. There is a one-time allowance for a new rigid cannula placement. Soft catheter placements or replacements, usually done through an existing burr hole and always done using a stylet with image guidance, do not count against this limited number of rigid cannula passes. There is no limit to the number of soft catheter placements or replacements as long as stability requirements are met. Occasionally it may be necessary to create a new burr hole/trajectory to access the clot. This will be done only after consultation with the Surgical Center. Repeat CT scan and upload DICOMs of the final catheter placement in the clot into the EDC for Surgical

Center review and approval of catheter location in residual hematoma prior to dosing.

The catheter is then tunneled subcutaneously, connected using sterile technique to a three-way stopcock and then to a closed drainage system. Level the drainage bag to zero.

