**Safety Monitoring and Recruitment Suspension Rules.** Safety events above pre-specified thresholds will trigger “a suspend recruitment and review “by the DSMB to investigate the presumed cause and impact of these events. Such events are initially reviewed by a Data Coordinating Center (DCC) staff member to determine if an event threshold has been reached at which time the study investigators and the DSMB will be notified. The thresholds triggering such a review are: 30-day mortality > 60%, a MIS+rt-PA related symptomatic bleeding rate > 25% (events identified within the first 30 days and assessed as occurring during active treatment or during the 72 hours after treatment will be monitored), first week operative death rate > 10%, and a procedure-related infection rate > 15% (over the initial 30 days). If any of these SAEs are attributable to the intervention (catheter insertion or manipulation, or rt-PA injection), the study will be suspended for a complete safety and efficacy review.

**Efficacy Monitoring and Recruitment Suspension Rules.** Interim analyses for safety will occur after 125, 250, 375 and 500 subjects are enrolled. One interim look at efficacy and futility will occur after 375 subjects are enrolled. These analyses will be based on ‘Brien-Fleming’ stopping boundaries for efficacy and more aggressive (i.e., more likely to stop if there is no early signal of benefit) stopping boundaries for futility.(Jennison C, Group sequential methods with applications to clinical trials. Boca Raton, FL. Chapman & Hall/CRC Press, 2000.)

**9.1.1. Randomization.** Subjects will be randomized to MIS+rt-PA surgery: medical management using a covariate-adaptive design similar to that used for the CLEAR III trial. The goal of this randomization scheme is to obtain an improved balance across study arms in the number of subjects with certain pre-randomization variables that are strongly predictive of the functional outcomes

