14.2. Total SAEs at 30 Days

Mortality attributed to MIS+rt-PA treatment plus disease-associated adverse events are similar to the morbidity and mortality attributed to medical management in the first 30 days. Analyses: For initial evaluations, differences between the MIS+rt-PA intervention and medical management groups will be examined using a logistic regression model.

14.3. Summary of Adverse Events and Serious Adverse Events by MedDRA Code and Grouped by Organ System

All AEs and SAEs are summarized by type and by treatment group in terms of frequency of the event, number of subjects having the event, timing relative to randomization, severity (mild, moderate, severe), and relatedness to the study treatment (definitely, probably, possibly, definitely not). At the end of the study, the cumulative incidences of these events will be compared between the two treatment groups using Fisher's exact test. Statistically significant differences between the treatment arms will be assessed after adjustments for multiplicity in the case of individual SAE/AE diagnoses and MedDRA codes. Additionally, generalized linear mixed models for binary data will be used to examine AE and SAE probabilities between treatment groups while accounting for potential confounders and site-clustering effects.

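### The causality guideline contradicts itself for harm from the MIS procedure: its Yes/No tests name rt-PA only, its grades name both, and its top two grades call for a withdrawal response that some events cannot show

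*Protocol*

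**What the plan says.** Protocol 10.4.2 (Assessment of Adverse Events) has each event described by its suspected relationship to the MIS procedure and to rt-PA. It gives each cause its own window: events more than 7 days after the procedure, or more than 72 hours after the last dose, are not expected to be called related. The investigator and/or Medical Monitor then chooses *Unrelated*, *Possibly*, *Probably* or *Definitely related*. The purpose of the text that follows is stated: "To ensure consistency of AE and SAE causality assessments, investigators should apply the following general guideline".

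That guideline has two lead-in tests, Yes and No, with the grades listed beneath them. The No test includes this limb: "and/or the AE has no plausible temporal relationship to rt-PA administration". *Definitely related*, under Yes, says: "The adverse event has a temporal relationship to the MIS procedure or rt-PA administration(s) and resolves when rt-PA administration is discontinued".

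Two design features create time and subjects without drug. After catheter placement, "a six-hour post-surgical stabilization period is required prior to first injection of rt-PA". Some surgical subjects never receive rt-PA: Protocol 5.1.2 and Section 8 (item 2) each describe post-aspiration clot volumes at which dosing is not given.

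Relatedness is used later. Protocol 9.1 (Safety Monitoring and Recruitment Suspension Rules) says: "If any of these SAEs are attributable to the intervention (catheter insertion or manipulation, or rt-PA injection), the study will be suspended".

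**The concern.** The purpose of the guideline is that different sites grade the same event the same way. In a trial of surgery plus drug, the harms most likely to come from the surgery are bleeds along the cannula or catheter path and early operative complications. These can occur before any drug is given. If the wording handles such events inconsistently, or holds irreversible ones at a low grade, relatedness becomes least reliable for the events that matter most to the safety review.

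The items that use relatedness are:
- the suspension step quoted above
- the MIS+rt-PA-related bleeding threshold (25%) and the procedure-related infection threshold (15%) in Protocol 9.1 and SAP 2.3.2
- expedited IND reports of deaths, which under Protocol 10.4 need evidence of a causal link
- the adverse event tables by relatedness in Protocol 9.1.8.1 and SAP 14.3

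**Working it through.** No arithmetic applies, because the point concerns classification criteria. The criteria of Protocol 10.4.2, side by side:

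| Text | Cause it refers to | Withdrawal element |
|---|---|---|
| Introductory text | MIS procedure and rt-PA | none |
| Yes test (three limbs) | rt-PA only | one and/or option |
| No test (two limbs) | rt-PA only | none |
| *Possibly* | either | information may be missing |
| *Probably* | either | response to withdrawal listed |
| *Definitely* | either | resolution on stopping rt-PA listed |
| *Unrelated* (only grade under No) | cause must be neither | none |

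**Case A: operative or catheter-tract bleed before the first dose.**
- Yes: no limb is met, since no rt-PA has been given.
- No: met. There is no temporal link to rt-PA, and the cause is something other than rt-PA.
- *Unrelated*: fails, because the cause is the procedure.
- *Possibly*: its timing element is met, through the procedure.
- *Probably* and *Definitely*: no drug was present to withdraw when the event arose.

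The lead-in sends the event to No. The grades exclude the only No outcome and leave a Yes outcome open.

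**Case B: the same bleed in a surgical subject who is never dosed.** The result is the same, and there is no later dosing period against which withdrawal could be judged.

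**Case C: fatal bleed after dosing has begun.**
- Yes: can be met on timing.
- *Definitely*: fails, because the event does not resolve.
- *Probably*: fails on a literal reading, because there is no response to withdrawal.
- *Possibly*: the highest grade open. It is worded for events where another cause may be responsible, so a fatal bleed with no other apparent cause fits it poorly.

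The withdrawal element does not look incidental. *Possibly* tolerates missing withdrawal information, and *Probably* waives rechallenge but not dechallenge.

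**Where the grade matters, and where it does not.** Three routes do not depend on the difference between *Possibly* and the higher grades. *Possibly* is enough for reporting to the coordinating center (Protocol Section 7) and for the 7-day and 15-day reports (Protocol 10.4). All cerebral bleeds are medical events of interest and get the same review as an SAE (Protocol 10.4.1). The DSMB's split of complications at 24 hours after catheter placement (Protocol 10.3.1) uses time alone. The 7-day and 15-day reports are therefore affected only if an event is coded *Unrelated*. The items listed under the concern remain exposed.

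The level names also differ: the tables in Protocol 9.1.8.1 and SAP 14.3 call the lowest level definitely not, where 10.4.2 has *Unrelated*.

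**The case against.** The best defence is that 10.4.2 is a general guideline that asks which grade best describes the event, applied by an investigator with Medical Monitor review. It is not a strict checklist. The introductory text and all four grades name the procedure, so a sensible investigator would not call an operative bleed *Unrelated*. *Probably* mentions withdrawal without naming rt-PA. The mortality thresholds carry no relatedness condition. The bleeding threshold is qualified by a time window, and Protocol 10.3.1 speaks of attribution at a 95% confidence level, which is not a site grade.

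Much of this stands, and it rules out four stronger readings that a reader might infer:
- **The whole rule tests rt-PA only.** Only the Yes and No lead-ins do.
- **Pre-dose surgical bleeds are coded *Unrelated*.** That grade excludes events caused by the procedure. The text is contradictory, so the coding is unpredictable.
- **The safety comparison is biased in favor of MIS+rt-PA.** Hypothesis 1b (Protocol 9.1.7) and SAP 14.1 speak of procedure-related events, but the specified test compares arm rates by SAE type against tolerances of 10% or 5%. SAP 2.3.1 lists all-cause mortality, symptomatic bleeding and infection rates.
- **The 25% bleeding threshold would be missed.** The documents give no share of bleeds before the first dose. Rebleeding in randomized surgical subjects in phase II was 3.7% (Protocol 2.2). Appendix 5 gives shares of events, not of subjects, and does not separate symptomatic bleeds.

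Nor is it established that brain infections can never reach the higher grades, since both phase II cases resolved.

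Judgement and central review lessen the defect without removing it. A guideline written for consistency should not support two answers for the same operative bleed.

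**Conclusion.** The concern holds as an internal contradiction plus a withdrawal criterion that some events cannot meet. For procedure-caused events before the first dose or in never-dosed subjects, the lead-in tests and the grades give different answers. Read literally, those events and fatal events cannot rank above *Possibly*, and a fatal bleed with no alternative cause fits no grade well.

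The effect on this trial cannot be computed: the documents give no count of pre-dose, never-dosed or fatal bleeds and do not show how sites graded them. The conclusion rests on a literal reading of the criteria. It also assumes that the later uses of related, procedure-related and attributable draw on 10.4.2, which gives the only graded relatedness definitions in the two documents; no passage states that link for the thresholds. The correction is worth making because the wording is wrong on its face and cheap to repair.

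**What to change.** In Protocol 10.4.2, state the Yes and No tests twice, once for the MIS procedure (including catheter placement and manipulation) and once for rt-PA. Record one causality judgement for each. The introductory text already asks about both causes, but the data entry form is not in the documents, so check whether it holds two fields.

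Apply the withdrawal criterion in *Probably* and *Definitely* only to events judged against rt-PA where a response can be assessed. Grade other events, including fatal ones and those judged against the procedure, on timing, location and absence of an alternative cause. Use the same four level names in Protocol 9.1.8.1 and SAP 14.3, and say which judgement feeds the related bleeding count, the procedure-related infection count and the suspension step.

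Re-review surgical-arm events already coded *Unrelated* that arose before the first dose or in never-dosed subjects.

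The cost is a wording change to the protocol and the data entry guidance, some re-review work, and somewhat more events counted as related.
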